7.0 STUDY VISITS

All study visits, assessments and procedures should be completed as indicated per the SOE

7.1 Visit and Assessment Windows

For those procedures for which a specific time point post dose is required (e.g., systemic exposure blood draws), the protocol refers to nominal times. Actual times for such assessments are to be recorded in the source documentation and in the eCRFs, and if any time points are

missed, the reasons are also to be recorded. For more details, please refer to the case report form completion guidelines.

Visits and/or assessments can be completed over multiple, non-consecutive days.

All efforts should be made to prevent missing data. Therefore, deviations from the treatment cycle (and subsequent assessments) may be justified in some cases (e.g., if an AE makes treatment impossible at the scheduled dosing day). In exceptional cases, e.g., related to the significant restrictions in site activities or subject's ability to travel to sites for visits as occurring related to the COVID-19 pandemic, extensions of the visit window or alterations in the SOE can be approved by the Medical Monitor. Such extensions of the visit window will be documented as protocol deviations. Still, sites should make every reasonable effort to complete scheduled visits within the time windows defined in this protocol.

7.2 Screening

Prior to or at the first Screening visit a sample for gene sequencing analysis will be obtained (see Section 8.5 for further details). In case the sample for gene sequencing analysis will be obtained prior to the first Screening visit, a separate Informed Consent Form (ICF) and/or assent is available for this purpose (see Section 12.2).

During the screening period, subjects will be assessed according to the eligibility criteria and specified assessments conducted, as presented in the SOE. Subjects who have been identified as screen failure may be rescreened if, in the opinion of the Investigator, there is a reasonable chance that the subject may become eligible at a later timepoint. If the decision is taken to rescreen a subject, the subject will need to be re-consented and will obtain a new subject number.

For all subjects, screening should be conducted in a stepwise manner so that eligibility is confirmed first by less intensive assessments. More intensive assessments are to be conducted once eligibility by other criteria have been confirmed to minimize risk and burden.

7.3 Dosing and Follow-up Visits

The timing of dosing and follow-up visits is outlined in the SOE

Study treatment

will be administered by unmasked qualified ophthalmologists.

All follow-up study visits, assessments and procedures should be completed as indicated per the SOE. All efforts should be taken to prevent missing data. Deviations from the treatment cycle (and subsequent assessments) may be justified in some cases (e.g., if an AE makes treatment impossible at the scheduled dosing day [see also Section 7.1]). Subjects will be assessed for safety, tolerability, and efficacy at follow-up visits with all ophthalmic assessments performed on both the TE and CE.

7.4 End of Study Visit & Roll Over to Open Label Extension Study

8.0 STUDY ASSESSMENT PROCEDURES

All clinical assessments (including all efficacy and safety assessments) will be performed by masked staff. Clinical monitoring during and right after administration of study treatment will be performed by an unmasked IVT physician (see also Section 4.2.1.3).

Eligible subjects must complete all Screening examinations. If a subject is unable to complete a specific assessment, this should be recorded in the eCRF and the subject's ability reassessed at the next specified visit. All attempts at performing assessments should be recorded in the eCRF. Any assessment may be repeated if the results are considered unreliable or of unacceptable quality by the Investigator.

8.1 Efficacy

Efficacy assessments include BCVA, LLVA, SD-OCT, microperimetry, FST and PROs. A central reading center, utilizing evaluators masked to treatment assignment, will assess microperimetry, FST, and SD-OCT. See the Study Reference Manual and Imaging Procedure Manual for further information on these assessments.

Subject's assessment of disease severity will be assessed by PGI-S, and assessment of any improvement or decline in clinical status will be assessed by PGI-C.

8.2 Safety

Safety assessments to monitor for AEs include ophthalmic examinations, laboratory evaluations, and SD-OCTs. Assessments will be conducted as indicated by the SOE

8.2.1 Adverse Events

Information regarding occurrence of AEs will be captured throughout the study. Duration (start and stop dates), severity/grade, outcome, treatment, and relationship to study drug will be recorded. Refer to Section [9.0](#) for further details.

8.2.2 Laboratory Evaluations

All laboratory evaluations will be conducted at a central laboratory. Reference ranges for all laboratory parameters are provided in the Laboratory Manual. See [Appendix 2](#) for a list of laboratory tests to be conducted.

Serum chemistries will include sodium, potassium, chloride, bicarbonate, blood urea nitrogen (BUN), creatinine, glucose, calcium, phosphorus, alanine aminotransferase (ALT), aspartate aminotransferase (AST), gamma-glutamyl transferase (γ GT), C-reactive protein (CRP), alkaline phosphatase (ALP), total and direct bilirubin, lactic dehydrogenase (LDH), albumin, and total protein. Estimated glomerular filtration rate (eGFR) is to be calculated using the Chronic Kidney Disease Epidemiology- Collaboration Creatinine Equation 2009 calculation for adult subjects and the Bedside Schwartz equation, according to the recommendation from National Institutes of Health/National Institute of Diabetes and Digestive and Kidney Diseases, for pediatric subjects.

Hematology will include a complete blood count (CBC): CBC with absolute differential (hematocrit, hemoglobin, white blood cell count [WBCs], red blood cell count, neutrophils, lymphocytes, monocytes, eosinophils, basophils, platelet count).

Coagulation panel: prothrombin time and International Normalized Ratio (INR).

Approximately 80 mL of blood will be drawn over the course of the entire study for laboratory evaluations, systemic exposure and immunogenicity.

For female subjects of childbearing potential, a pregnancy test will be performed as indicated by the SOE
-and is recommended at any visit that may warrant a pregnancy test.

Eligibility of the subject to participate in the study is based in part on safety signals that may be indicated by laboratory values.

Repeat laboratory tests are permitted to confirm potentially spurious values or false positive results, at the discretion of the Investigator. Repeat analysis results for any laboratory assessments that are eligibility criteria should be discussed with the Medical Monitor prior to subject inclusion.

8.2.3 Ophthalmic Examinations

Ophthalmic examinations include slit lamp biomicroscopy, intraocular pressure, and dilated fundus examination and will be performed as indicated per the SOE

Further details on the procedures for ophthalmic examinations are in the Study Reference Manual.

8.2.4 Spectral Domain Optical Coherence Tomography

Changes in SD-OCT findings,

All SD-OCT scans should be performed in accordance with the procedures outlined in the Imaging Procedure Manual.

8.3 Systemic Exposure

Blood samples for systemic exposure analysis of ultevursen will be collected from all subjects as indicated per the SOE (see Section 8.2.2)

8.4 Immunogenicity

Blood samples for assessment of immunogenicity will be taken as indicated per the SOE (see Section 8.2.2 and stored for potential later quantification.

8.5 Gene Sequencing

A genotyping report is required for eligibility.

Separate informed consent may need to be obtained per local requirements. A blood or saliva sample for genotyping and gene sequencing should be obtained at or prior to the Screening Visit. In case the sample for gene sequencing analysis will be obtained prior to the first Screening Visit, a separate ICF and/or assent is available for this purpose (see Section 12.2).

9.0 ASSESSMENT OF SAFETY, ADVERSE EVENTS AND SERIOUS ADVERSE EVENTS

All subjects who receive study treatment will be assessed for safety.

Investigators are responsible for monitoring the safety of subjects who have entered this study and for alerting the Sponsor regarding any event that seems unusual, even if this event may be considered an unanticipated benefit to the subject. The Investigator is responsible for appropriate medical care of subjects during the study and may add unscheduled visits, additional exams/tests for safety purposes.

9.1 Data Monitoring Committee

An independent DMC will provide safety oversight for the study. A DMC operational charter will be finalized, and an initial organizational meeting held prior to screening of the first subject.

Reference is also made to Sections 4.2.3 and 4.2.4.

9.2 Definitions of Adverse Event, Serious Adverse Event, and Suspected Unexpected Serious Adverse Event

9.2.1 Adverse Events

An AE is any untoward medical occurrence associated with the use of a drug in humans, whether considered drug related or not. Adverse events can include any unfavorable, noxious, unintended sign, symptom, or disease temporally associated with use of a study drug or other protocol-imposed intervention, regardless of attribution. Adverse events may be spontaneously reported

by the subject, discovered by Investigator questioning, or detected through laboratory test, or other means.

Adverse events include:

- Pre-existing medical conditions judged by the Investigator to have worsened in severity or frequency or changed in character during the protocol-specified AE reporting period (as specified in Section 9.4.1)
- Adverse events not previously observed in the subject that emerge during the protocol-specified AE reporting period (as specified in Section 9.4.1)
- Complications that occur as a result of protocol-mandated interventions
- Adverse events that occur prior to study treatment that are related to a protocol-mandated intervention (e.g., invasive procedures such as blood draws, sedation prior to IVT injection)

9.2.2 Serious Adverse Events

An AE is considered “serious” if, in the view of Investigator, it results in any of the following outcomes:

- Death
- Life-threatening AE. This definition implies that the subject, in the view of the Investigator, is at immediate risk of death from the event as it occurred. It does not include an event that, had it occurred in a more severe form, might have caused death
- Inpatient hospitalization or prolongs existing hospitalization, except for planned hospitalization
- Persistent or significant disability/incapacity (i.e., the AE results in substantial disruption of the subject’s ability to conduct normal life functions)
- Congenital anomaly or birth defect. This serious criterion applies if a congenital anomaly/birth defect is diagnosed in a child born to a female subject, or a female partner of a male subject exposed to the study drug
- Other important medical events. Medical and scientific judgment should determine whether an AE should be classified as serious in other situations, such as important medical events that may not be immediately life threatening or result in death or hospitalization but may jeopardize the subject or require intervention to prevent one of the outcomes listed in the definition above.

All AEs that do not meet any of the criteria for serious should be regarded as non-serious AEs. Surgery for lens opacity removal (lens replacement) is not considered a serious AE as it does not require the subject be admitted to a hospital unit based on the nature of the surgery. Even in the

case where the subject may be hospitalized for convenience, or a subject is too frail to make the commute back and forth to the surgical center, it is still not a Serious AE. The terms “severe” and “serious” are not synonymous. Severity refers to the intensity of an AE (as in mild, moderate, or severe pain); the event itself may be of relatively minor medical significance (such as severe headache) (see Section 9.3.1). “Serious” is a regulatory definition and is based on subject or event outcome or action criteria usually associated with events that pose a threat to a subject’s life or vital functions. Seriousness (not severity) serves as the guide for defining regulatory reporting obligations.

Severity and seriousness should be independently assessed when recording AEs and serious adverse events (SAEs) on the AE eCRF and SAE form.

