2.3 Benefit Risk Assessment

Retinitis Pigmentosa is a group of inherited eye disorders causing slow photoreceptor degeneration, leading to progressive vision loss. Affected patients first experience defective dark adaption, peripheral visual field loss when photoreceptor degeneration progresses, and eventually have only a residual central island of vision, which ultimately progresses to complete blindness. There are currently no approved therapies for the treatment of RP patients with mutations in exon 13 of the *USH2A* gene and disease management is supportive. They may receive adaptive support, when necessary. In addition, patients usually receive genetic counselling on the risks of passing the condition on to their children and regular medical follow up. A significant unmet medical need exists in this sight-threatening condition.

The design of this study has been selected to provide a sufficient benefit-risk ratio to justify the participation of subjects. Planned doses are expected to result in retinal concentrations in the efficacious range. In addition, multiple measures are incorporated to ensure the safety of participating subjects.

To address the potential risks defined in the toxicology studies, the reported risks from oligonucleotides administered by IVT injection, and the risks associated with the IVT injection procedure, extensive monitoring to protect subject safety is incorporated in this study. This will include assessments of subjects' ophthalmic function and anatomy, in particular, monitoring of anterior, intermediate and posterior segment inflammation by slit-lamp biomicroscopy, clinical lens grading using the Age-Related Eye Diseases Study (AREDS) Clinical Lens Grading System, and monitoring for retinal changes by OCT and dilated fundus examinations. This extensive clinical monitoring provides a means to allow early detection of potential AEs, such as macular edema, changes in BCVA and IOP, detection of intraocular inflammation, lens opacities, and retinal structural modifications. In addition, the visit schedule is designed to monitor subjects one day following IVT injection and a second time within 1 week of IVT injection to monitor for signs of endophthalmitis and intraocular inflammation, consistent with guidelines for IVT injections ([Avery 2014](#)).

While the number of subjects is small, these results, and the positive benefit-risk assessment support continued clinical testing of ultevursen.

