2.5 Measures to Minimize Bias

To facilitate interpretation of clinical data, inclusion of randomized, concurrent parallel control groups is recommended for clinical studies whenever possible. Masking of participating subjects, treating physicians and study staff is of particular importance when subject effort or perception

could bias evaluation of study endpoints, such as for measurement of visual acuity ([Glassman 2012](#)).

IVT injection is a well-established route of administration within ophthalmic indications that permits targeting of the therapeutic agent to the eye, while minimizing systemic absorption. IVT injection is used in several products for the chronic treatment of ophthalmic diseases (e.g., Lucentis®, Eylea™, Macugen®) and the risk of complications is low when injections are performed by trained ophthalmologists ([AAO 2015, Avery 2014](#)).

However, potentially severe complications to IVT injections exist, including endophthalmitis, intraocular inflammation, cataract, retinal detachment, and vitreous hemorrhage. Although the risk of severe complications is small, it is well documented ([Jager 2004](#)). Therefore, while IVT injection of the vehicle alone is theoretically feasible as a placebo control, it is not considered ethical since the physical properties of such an injection do not have potential therapeutic benefit. Hence, placebo injections will not be administered in this study to preserve subject safety.

Other possibilities than placebo injections to effect masking include alternative dosing regimens, alternative dose levels, and existing products approved for the indication being sought. There are no existing approved products for the indication under investigation.

Use of sham-procedures (i.e., no penetration of the globe) to mask subjects to treatment assignment in studies of products administered via IVT injections eliminates the risk of complications due to injection in the control arm. The sham-procedure, which closely mimics the injection procedure used for product delivery can effectively mask participants to treatment assignment; however, the masking effect is less pronounced in the case that a single subject receives both the real and sham injections in their 2 eyes ([Glassman 2012](#)).

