When recording a death, the event or condition that caused or contributed to the fatal outcome should be recorded as a single medical concept. For example, if death resulted from respiratory failure, the AE recorded should be “Respiratory Failure”, and the outcome of the AE would be “Death”. If the cause of death is unknown and cannot be ascertained at the time of reporting, record “unexplained death” on the AE eCRF and SAE form.

e. Preexisting Medical Conditions

A preexisting medical condition is one that is present at the start of the study. Such conditions should be recorded on the Medical History eCRF.

A preexisting medical condition should be recorded as an AE or SAE only if the frequency, severity, or character of the condition worsens during the study. When recording such events on an AE eCRF and SAE form (if applicable), it is important to convey the concept that the preexisting condition has changed by including applicable descriptors (e.g., “more frequent headaches”).

f. Hospitalization, Prolonged Hospitalization or Surgery

Any AE that results in hospitalization or prolonged hospitalization should be documented and reported as an SAE unless specifically instructed otherwise in this protocol.

g. Pregnancy

If a female subject or a female partner of a male subject becomes pregnant during study participation of the female subject or the male partner, a Pregnancy Report form should be completed and faxed to the Sponsor within 24 hours of learning of the pregnancy, using the fax numbers listed in the Study Reference Manual.

Abortion, whether therapeutic or spontaneous, will also be reported on a Pregnancy Report form and faxed to the Sponsor. Refer to the Study Reference Manual for forms and complementary reporting information. If the abortion meets seriousness criteria (see Section 9.2.2, Serious Adverse Event Definition), this information will be captured on the AE eCRF and SAE form (if applicable).

Pregnancy should be followed up until after delivery, and any events to 3 months post-partum or termination of the pregnancy. Any congenital anomaly/birth defect in a child born to a female subject or to a female partner of a male subject exposed to the study drug should be recorded and reported as an SAE.

h. Special Situations Reporting

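### Protocol 9.2.2 rules lens-removal surgery non-serious for a reason that covers only hospitalization, so a lens opacity leading to surgery can escape the other seriousness criteria

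*Protocol*

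**What the plan says.** Protocol Section 9.2.2 lists six outcomes, any one of which makes an AE serious in the Investigator's view: death, a life-threatening event, inpatient or prolonged hospitalization (other than planned), persistent or significant disability/incapacity, congenital anomaly, and other important medical events. The last covers events that do not lead to hospitalization but "may jeopardize the subject or require intervention to prevent one of the outcomes listed in the definition above". The complement is then stated: "All AEs that do not meet any of the criteria for serious should be regarded as non-serious AEs".

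The next two sentences carve out one procedure. The first reads: "Surgery for lens opacity removal (lens replacement) is not considered a serious AE as it does not require the subject be admitted to a hospital". The second extends this to a subject who is in fact admitted, either for convenience or because "a subject is too frail to make the commute back and forth to the surgical center, it is still not a Serious AE".

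Cataract is a foreseen event in this trial. Section 2.5 says that "potentially severe complications to IVT injections exist, including endophthalmitis, intraocular inflammation, cataract, retinal detachment, and vitreous hemorrhage", and adds that a sham procedure removes injection complications from the control arm. Section 2.3 includes lens opacities among the potential AEs that clinical monitoring, with AREDS lens grading, is meant to detect early.

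**The concern.** A rule that any one of six criteria suffices cannot be switched off by an argument about one of them. As worded, the carve-out invites a site to stop at the word surgery and tick non-serious, without asking whether the lens opacity behind it caused significant disability or was an important medical event.

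Four things in the documents depend on that tick:

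- **Tabulation.** Protocol 10.9.1 tabulates serious AEs by treatment group, and SAP 5.6 lists an SAE summary.
- **SUSAR assessment.** Under Protocol 9.2.3 an event must be serious to qualify.
- **Follow-up.** Under Protocol 9.4.1, SAEs related to study treatment are followed until they resolve, return to baseline or stabilize, or the subject is lost to follow-up. Non-serious AEs are followed only to the end-of-study visit.
- **Notification.** Protocol 9.5 sets a 24-hour route for SAEs and AESIs. A non-serious event gets it only if it is an AESI.

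The population makes the question a live one. Subjects enter with treated-eye BCVA between 30 and 73 letters (Protocol 5.3.1, criterion 5), and the disease eventually leaves only a central island of vision (Protocol 2.1). Whether a lens opacity substantially disrupts normal function is a case-by-case judgment for such subjects.

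**Working it through.** No arithmetic applies: the point concerns a definition, and neither document gives a rate of cataract or lens surgery. The check sets the stated reason against each criterion in Protocol 9.2.2.

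| Criterion in 9.2.2 | Does the absence of a need for admission settle it? |
|---|---|
| Death | Not addressed; not at issue here |
| Life-threatening | Not addressed; not at issue here |
| Inpatient or prolonged hospitalization | Yes, this is the one criterion the reason speaks to |
| Persistent or significant disability/incapacity | No; it turns on function, not on where surgery is done |
| Congenital anomaly | Not addressed; not at issue here |
| Other important medical event | No; it expressly covers events without hospitalization |

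So the reason addresses one criterion of six. Two of the other five could plausibly be met by a lens opacity that impairs vision, and the reason does not touch either.

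**Is the exclusion conditional?** The first sentence has no qualifier. The second, on convenience or frailty, widens the exclusion. Neither says that the remaining criteria still apply.

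**Does another section restore the test?** Section 9.4.3(f) says: "Any AE that results in hospitalization or prolonged hospitalization should be documented and reported as an SAE unless specifically instructed otherwise in this protocol". The carve-out is such an instruction, so this rule gives way to it. Section 9.2.2 also asks for severity and seriousness to be assessed independently, but that separates two scales; it does not say which criteria to apply to a case of lens surgery.

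**Does the exception for planned hospitalization explain the rule?** Only in part. That exception belongs to the hospitalization criterion, so it cannot dispose of the others. Planned intraocular surgery in either eye is also an entry exclusion (Protocol 5.3.2, criterion 9), so lens surgery during the study would ordinarily be unplanned at entry.

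**What remains visible if a case is classed as non-serious?** SAP 5.6 summarizes ocular TEAEs by eye, SOC and PT, and SAP 5.7 lists ocular AEs by subject. The event is not lost from safety reporting. What it loses is SAE status and what depends on that status.

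**The case against.** The strongest reply is that the sentence exempts a procedure, not an event. The AE is the lens opacity, and nothing in 9.2.2 says that a lens opacity cannot be serious. A careful Investigator could exempt the surgery and still judge the opacity against all six criteria. This stands, and it limits the claim: misclassification is possible, not certain. It does not remove the problem, because the text does not tell sites to make that distinction.

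A reader might infer that lens surgery is exempt whatever the reason for admission. The second sentence covers only convenience and frailty. Admission for a complication of the surgery is not mentioned; a complication would normally be a separate AE under 9.4.3(a).

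A reader might also infer that the rule hides harm in the ultevursen arms relative to sham, since only injected eyes face injection-related cataract. The documents do not show this. Opacities below the exclusion threshold are allowed at entry (Protocol 5.3.2, criterion 7), so lens surgery can arise in any arm and need not be caused by treatment. SAP 5.4 names only the two ultevursen groups and all subjects as summary columns, and SAP 6 plans no formal analysis. No planned comparison with sham is shown to be biased.

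The SUSAR consequence is also conditional. Protocol 9.2.3 further requires suspicion of a reaction to the study drug and unexpectedness against reference safety information that is not in these documents. Finally, the content of Section 9.2.4 on AESIs is not in the public text. If lens opacity is listed there, 24-hour notification and a separate SAP output are kept; SAE status is not.

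**Conclusion.** The concern holds as an internal conflict in Protocol 9.2.2. An unconditional exclusion rests on a reason that covers one seriousness criterion, while the same section makes any one of six sufficient. Sites can therefore class a lens opacity leading to surgery as non-serious without testing disability/incapacity or important medical event. The possible losses are SAE tabulation, SUSAR assessment and extended follow-up of related SAEs.

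No size is attached. It is tempting to take an assumed number of surgeries over the 27 + 27 = 54 subjects planned for injection and report the result as the share missing from the SAE table. Neither document supports any numerator, 54 is a planned figure in a study that SAP 6 says was stopped early, and not every lens replacement would meet another criterion.

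The conclusion assumes that at least some sites would read the exclusion of the surgery as covering the event that led to it. It is worth correcting because the event is tied to a named complication of the injection and the correction is cheap.

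**What to change.** Reconcile the carve-out with the criteria list by replacing both lens-surgery sentences in Protocol 9.2.2 with one:

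*Admission solely for elective lens-removal surgery, including for convenience or frailty, does not by itself meet the hospitalization criterion; the underlying lens opacity is assessed against all other criteria in this section.*

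Both sentences need replacing together, since cutting only the closing clause of the second would leave it incomplete. The new wording presumes no case to be serious; it limits the exemption to the criterion it reasons about.

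Because the study was stopped early, new wording alone may reach few future events. Any lens-surgery cases already recorded should also be reviewed against all the 9.2.2 criteria before database lock, so that the SAE table reflects the result.

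The cost is one sentence, a notice to sites and a short case review. The downside is a few more SAE forms and a possibly less favourable SAE count.
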